5.4 OUTCOME DEFINITIONS

The primary outcomes are the absolute differences in sensitivity and specificity between pairs of index tests: vital signs (Day 0) vs vital signs (Day 0) + lactate (Day 0), and vital signs (Day 0) + lactate (Day 0) vs vital signs (Day 0 and Day 1) + lactate (Day 0 and Day 1).

Secondary outcomes include:

- The absolute differences in sensitivity and specificity between vital signs (Day 0) alone and vital signs (Day 0) + lactate (Day 0) for maternal sepsis assessed at Day 0 only;
- The predictive value of vital signs (Day 0) alone compared to that of vital signs (Day 0) + lactate (Day 0) in those without sepsis at baseline, for maternal sepsis assessed at Day 1 only;
- The predictive value of vital signs (Day 0) alone compared to that of vital signs (Day 0) + lactate (Day 0) for the occurrence of severe morbidity and mortality from infection (WHO "severe maternal outcomes") (4), which is assessed daily until day 14 or discharge or death, if sooner;
- The sensitivity and specificity of vital signs (Day 0) + lactate (Day 0) and vital signs (Day 0 and Day 1) + lactate (Day 0 and Day 1) by: pregnancy status (pregnant or postdelivery/post miscarriage/post-abortion), source of sepsis (genital tract or nongenital tract) and condition on admission (stable or critical);
- The sensitivity and specificity of the primary index test comparisons including those women discharged early, assuming that they did not have sepsis;
- In an exploratory analysis, the sensitivity and specificity of each index test will be estimated based on different threshold values for lactate;
- To explore the use of an alternative reference standard, in which the SOFA score is modified to use maternity specific ranges for creatinine and platelet concentration, an independent expert review group will examine all cases with discordant results to adjudicate based on clinical features, clinical management, response to treatment and outcomes, if the case fitted the WHO definition of maternal sepsis. The pattern of discrepant results will be investigated descriptively.
 - 5.5 SAMPLE SIZE

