We aim to recruit 500 women to the study in total. In computing sample sizes, we estimated that an increase of 20% in sensitivity would be both feasible and clinically important. This equates to detecting an additional sepsis case for every 5 women who have sepsis. Assuming a prevalence of 40%, defining statistical significance at the 5% level and ensuring 90% power, up to 346 participants in total would ensure we are appropriately powered across a range of baseline sensitivities between 30 and 60% when vital signs alone are used. It is important to also estimate specificity to detect any important increase in false positives. With 200 patients without sepsis, the specificity of each test will be estimated with 95% confidence interval (CI) width of 15 percentage points for a specificity of 75% and width less than 10 percentage points for a specificity of 90%. This is adequate precision to allow important changes to be estimated. Allowing for loss to follow-up and missing / laboratory results, we consider an initial sample size of 500 as appropriate to allow the study to have adequate power to test these hypotheses. This number of cases will be feasible to collect within 12 months, based on current infection rate data from all sites.

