6 STATISTICAL PRINCIPLES

6.1 LEVELS OF CONFIDENCE AND P-VALUES

All confidence intervals presented will be 95% and two-sided. All applicable statistical tests will be two-sided, with a p-value of ≤ 0.05 considered to be statistically significant.

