7.3 FINAL ANALYSIS

Primary analysis

We will estimate the sensitivity, specificity, positive predictive value (PPV) and negative predictive value (NPV) of the three index tests to detect sepsis assessed at Day 0 and Day 1. The 95% CIs for the estimates will be calculated using the Wilson method for proportions. To compare the accuracy of sepsis diagnosis by vital signs alone versus vital signs + lactate, we will fit separate generalized estimating equation (GEE) models for women with and without sepsis to estimate absolute differences in sensitivity and specificity, respectively. This approach exploits the paired nature of the data. We will compute absolute differences

in sensitivities and specificities from the GEE models using a post-estimation procedure with Cls computed using the delta method.

Secondary analyses

We will assess (a) index tests based on Day 0 only against Day 0 reference standard to determine immediate diagnostic value; (b) index tests based on Day 0 only against Day 1 reference standard in those without sepsis at baseline to determine short-term predictive value; and (c) index tests based on Day 0 only with occurrence of infection related "severe maternal outcome" (near miss or maternal mortality) (4) prior to hospital discharge to determine predictive value for severe morbidity or mortality (5) assuming that those women discharged prior to the Day 1 assessment did not have sepsis. Sensitivity, specificity, PPV, and NPV will be calculated for each test. In addition, for each of the analyses above, we will estimate absolute differences in sensitivity and specificity of vital signs alone versus vital signs (Day 0) + lactate (Day 0).

Pre-specified subgroup analyses will include pregnancy status (pregnant or postnatal) and illness severity to explore if the test accuracy of lactate in addition to vital signs alone varies by these subgroups.

Exploratory receiver operating characteristic (ROC) curve analyses will examine the effect of adjusting the threshold value for lactate on the sensitivity and specificity of the index tests.

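### SAP 5.5 misstates the precision for specificity: with 200 women without sepsis, the 95% CI at a specificity of 75% is about 12 points wide, not 15

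*SAP*

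**What the plan says.** Section 5.5 (Sample size) sizes the study on sensitivity and then turns to specificity: "With 200 patients without sepsis, the specificity of each test will be estimated with 95% confidence interval", with a "width of 15 percentage points for a specificity of 75% and width less than 10 percentage points for a specificity of 90" per cent. It then calls this precision adequate.

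Three other places bear on the figure:

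- Section 6.1: "All confidence intervals presented will be 95% and two-sided".
- Section 6.2: no adjustment for multiple testing, so nothing calls for a level wider than 95%.
- Section 7.3, primary analysis: intervals for the sensitivity and specificity of each of the three index tests are "calculated using the Wilson method for proportions".

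Section 5.4 defines the primary outcomes as differences: "The primary outcomes are the absolute differences in sensitivity and specificity between pairs of index tests".

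**The concern.** The width of an interval for one proportion is fixed by the number of women, the proportion, the confidence level and the method. The SAP gives all four, so a reader can recompute the stated width, and the 75% figure does not come out. Specificity is half of the primary outcome, and this sentence is the only numerical support in section 5.5 that enough women without sepsis will be available. If the true width were larger than stated, the claim of adequate precision would be in doubt. The check therefore has to establish both whether the figure is wrong and in which direction.

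**Working it through.** **Inputs.** n = 200 women without sepsis, specificity p = 75% or 90%, and stated widths of 15 points and under 10 points (section 5.5). Two-sided 95%, so z = 1.96 (section 6.1). Wilson method (section 7.3).

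**The stated figure at 75%.**

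Wald width = 2 × 1.96 × √(p(1 − p)/n) = 3.92 × √(0.75 × 0.25/200) = 3.92 × 0.03062 = 0.1200.

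Wilson width = 2z√(p(1 − p)/n + z²/(4n²)) / (1 + z²/n) = 3.92 × √(0.0009375 + 0.0000240) / 1.0192 = 0.1193, an interval of about 68.6% to 80.5%.

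| Method, n = 200 | Width at 75% (points) | Width at 90% (points) |
|---|---|---|
| Stated in SAP 5.5 | 15 | under 10 |
| Wilson | 11.9 | 8.4 |
| Wald | 12.0 | 8.3 |
| Exact (Clopper–Pearson) | 12.4 | 8.8 |
| Wald, continuity-corrected | 12.5 | 8.8 |
| Wilson, continuity-corrected | 12.4 | 8.9 |

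Agresti–Coull and Jeffreys intervals also round to 12 points at 75%. The 75% figure is not reproduced by any of the seven methods. The 90% figure is reproduced by all of them.

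**Could another input explain 15?**

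- *Another specificity.* The interval is widest at 50%. At n = 200 it is then 13.7 (Wilson), 13.9 (Wald) or 14.3 (exact), still short of 15.
- *Another n.* Solving the Wald formula for a width of 0.15 at 75% gives n = 3.92² × 0.1875/0.15² = 128. The exact method needs about 140. Neither number is in the SAP. The numbers without sepsis that follow from the SAP's 40% prevalence are 346 × 0.6 ≈ 208 and 500 × 0.6 = 300 (the latter before any losses). Their Wilson widths are 11.7 and 9.8 points, narrower than at 200.
- *Another confidence level.* At 98% the width is 14.1 to 14.6 points, and at 99% it is 15.6 to 16.1. The SAP says 95% in both 5.5 and 6.1.
- *A variance inflation.* Stretching 12.0 to 15 needs a factor of (15/12)² = 1.56. Applied at 90%, it gives 8.32 × 1.25 = 10.4 points, which breaks the second half of the same sentence.

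**Paired difference, for orientation only.** Under section 5.2 the combined Day 0 test is positive only if vital signs are positive too, and the two-day test is positive whenever the combined Day 0 test is. Each compared pair is therefore nested, and discordance runs one way. The variance of a difference d is then d(1 − d)/n, so the Wald 95% width is 3.92 × √(d(1 − d)/200). The SAP gives no value for d. For assumed values:

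| Assumed difference d (points) | Width (points) |
|---|---|
| 5 | 6.0 |
| 10 | 8.3 |
| 20 | 11.1 |

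**The case against.** The strongest reply is that the error does no harm. The true interval is narrower than stated: if 15 points was judged adequate, 12 is adequate as well. No analysis, decision rule or recruitment target depends on the figure, and the 90% half of the sentence is right. All of this stands and makes the point a small one. It does not make the figure correct.

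A second reply is that 15 was meant as a ceiling. It would then be true but loose. However, the sentence writes an upper bound only for the 90% case and a plain width for the 75% case, so 15 reads as a value.

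A reader might go further and infer that the precision statement concerns a quantity the study does not analyse, because the primary outcomes are paired differences. The document does not support that. Section 7.3 places the specificity of each single test, with a Wilson interval, inside the primary analysis, and section 5.5 says plainly that its figures are for each test. It is true that no precision is given for the paired difference. That is an omission, not a misstatement, and any figure for it rests on a difference in specificity that the SAP never states.

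**Conclusion.** The 75% figure is wrong as written. The width is about 12 percentage points (Wilson 11.9, Wald 12.0, exact 12.4), so the stated 15 overstates it by 3 points, or 3/12 = 25%. This rests only on the SAP's own n, specificity, confidence level and method.

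The 90% statement is correct. A reader might infer from a faulty precision figure that the study is too small for specificity. That does not follow, because the error runs in the safe direction and leaves both the adequacy conclusion and the target of 500 as they are. The point is a correction to the sample-size justification, of minor consequence.

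**What to change.** In section 5.5, replace the precision sentence with:

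*With 200 women without sepsis, the 95% Wilson CI for the specificity of each test is about 12 percentage points wide at a specificity of 75% and about 8 points at 90%.*

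If 15 points was meant as an upper limit, say so explicitly.

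Optionally, add the precision for the paired difference in specificity. Label it as an assumption and give a range, for example about 6, 8 and 11 points wide for differences of 5, 10 and 20 points with 200 women and nested tests.

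The cost is one sentence. Sample size, recruitment and analysis do not change.

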6 STATISTICAL PRINCIPLES

6.1 LEVELS OF CONFIDENCE AND P-VALUES

All confidence intervals presented will be 95% and two-sided. All applicable statistical tests will be two-sided, with a p-value of ≤ 0.05 considered to be statistically significant.

6.2 ADJUSTMENT FOR MULTIPLICITY

No adjustments will be made for multiple testing.

6.3 ADHERENCE AND PROTOCOL DEVIATIONS

Numbers and percentages by maternal sepsis status will be tabulated for the protocol deviations and violations.

7 ANALYSIS METHODS

7.1 DESCRIPTIVE STATISTICS

The demographic and clinical characteristics of women with and without maternal sepsis will be described. Continuous data will be summarised using mean and standard deviation if data are normally distributed, and median and interquartile range if data are skewed. Categorical data will be summarised using frequencies and percentages. The number of women with missing data will also be tabulated.

7.2 INTERIM ANALYSIS

Interim analyses will be conducted at 6 months during the trial recruitment. The analyses will include a description of key demographic and clinical characteristics of women with and without maternal sepsis and the estimate of prevalence of sepsis. Based on the estimated prevalence, the sample size requirements will be revisited to assess whether the target sample size needs to be adjusted. The completeness of variables used for the index and reference tests will be assessed, along with the quality of the data collection. The number and characteristics of the women missing a Day 1 assessment will also be assessed. The TOC Subgroup will consider these results, accruals, as well as any data from external trials to make an ongoing judgement on recommendations to be made according to their terms of reference.

7.3 FINAL ANALYSIS

Primary analysis

We will estimate the sensitivity, specificity, positive predictive value (PPV) and negative predictive value (NPV) of the three index tests to detect sepsis assessed at Day 0 and Day 1. The 95% CIs for the estimates will be calculated using the Wilson method for proportions. To compare the accuracy of sepsis diagnosis by vital signs alone versus vital signs + lactate, we will fit separate generalized estimating equation (GEE) models for women with and without sepsis to estimate absolute differences in sensitivity and specificity, respectively. This approach exploits the paired nature of the data. We will compute absolute differences

in sensitivities and specificities from the GEE models using a post-estimation procedure with Cls computed using the delta method.

Secondary analyses

We will assess (a) index tests based on Day 0 only against Day 0 reference standard to determine immediate diagnostic value; (b) index tests based on Day 0 only against Day 1 reference standard in those without sepsis at baseline to determine short-term predictive value; and (c) index tests based on Day 0 only with occurrence of infection related "severe maternal outcome" (near miss or maternal mortality) (4) prior to hospital discharge to determine predictive value for severe morbidity or mortality (5) assuming that those women discharged prior to the Day 1 assessment did not have sepsis. Sensitivity, specificity, PPV, and NPV will be calculated for each test. In addition, for each of the analyses above, we will estimate absolute differences in sensitivity and specificity of vital signs alone versus vital signs (Day 0) + lactate (Day 0).

Pre-specified subgroup analyses will include pregnancy status (pregnant or postnatal) and illness severity to explore if the test accuracy of lactate in addition to vital signs alone varies by these subgroups.

Exploratory receiver operating characteristic (ROC) curve analyses will examine the effect of adjusting the threshold value for lactate on the sensitivity and specificity of the index tests.

We will assess a modified SOFA score incorporating maternity specific ranges for creatinine and platelet concentration as an alternative reference standard. Following the recommendations of Bowyer et al (5), based on the findings of Larsson et al. (6), the serum creatinine cut off for the scores of 0, 1 or 2 have been adjusted to <90µmol/L, 90-120µmol/L or greater than 120µmol/L respectively. Based on a mean platelet count decrease of 17% during pregnancy (7), we will propose t modified cut offs for the scores of 0, 1, 2, 3 and 4 respectively (e.g. >=125, 83-124, 42-82, 17-41 and <17). This preliminary assessment, conducted after the main analysis, will follow a methodological approach we have used for test accuracy studies in tuberculosis and other diseases to compare reference standards (8). The approach involves considering women for whom the alternative reference standard gives discordant results compared to the SOFA score, and will involve two parts: (a) examination by an independent expert review group of all cases with discordant results to adjudicate based on clinical features, clinical management, response to treatment and outcomes, determining if the case fitted the WHO definition of maternal sepsis; (b) an investigation of the patterns in the discrepant results.

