2 BACKGROUND AND RATIONALE

Maternal sepsis can develop in pregnant women and women who have recently experienced pregnancy. Failure to rapidly recognise and treat maternal sepsis is a common factor identified in those women who die (1). In partnership with the WHO, the Global Sepsis Alliance, the UK Sepsis Trust, and other stakeholders, the study team developed the Fluids, Antibiotics, Source identification and control, Transfer and Monitoring (FAST-M) sepsis care bundle specifically for pregnant or recently pregnant mothers in a low resource setting, which should be acted upon in all women with suspected sepsis within one hour. However, there is still considerable uncertainty around the optimal "trigger" used to identify when further action is required by the health care team to prompt FAST-M initiation. A "trigger" should ideally be a sensitive measure that enables reliable and early identification of women who may benefit from the FAST-M bundle use. This needs to be balanced against the risks of an imperfect trigger resulting in false positives, impacting on already overstretched resources and distractions from other clinical priorities. Furthermore, there is the danger of over treatment if FAST-M is administered to patients who do not have sepsis.

Measurement of blood lactate forms a key part of sepsis management and risk stratification in current international guidelines from both National Institute for Health and Care Excellence (NICE) in the United Kingdom (UK) and the Surviving Sepsis Campaign. However, these guidelines were developed for non-pregnant populations in high income countries (2). It would be expected that in the substantially different population of pregnant women, in low-resource settings, that the test may perform differently.

The aim of the LACTATE study is to investigate if a lactate measurement has incremental benefit over conventional maternal vital sign assessment in the diagnosis of sepsis and identification of women at risk of severe morbidity or mortality in low resource settings. We will assess the diagnostic and prognostic accuracy of venous lactate measurement in maternity populations, in low resource settings, which is unknown.

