5.2 INDEX TESTS

The three index tests being evaluated are:

- 1) Vital signs at Day 0 (see Table 1)
- 2) Vital signs at Day 0 + lactate at Day 0
- 3) Vital signs at Day 0 and Day 1 + lactate at Day 0 and Day 1

The vital signs will indicate sepsis if one or more of the thresholds listed in Table 1 are exceeded. A lactate >2mmol/L will indicate sepsis. For tests combining vital signs and lactate, both will need to indicate sepsis to give a positive test result. For the test combining Day 0 and Day 1 measurements, a positive test will require the vital signs and lactate measurements to indicate sepsis at either Day 0 or Day 1.

Vital sign	Threshold
Respiratory Rate	>25 per minute
Heart rate	>120 beats per minute
Systolic Blood Pressure	< 90mmHg
Urine output	Less than 0.5ml/kg/hour
Mental state	Altered state

Table 1: Vital sign threshold values

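### For Day 0 vital signs versus Day 0 vital signs plus lactate, the both-positive rule fixes the sign of both primary differences, so excluding zero does not show that lactate adds information

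*SAP*

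**What the plan says.** SAP section 2 gives the aim: "to investigate if a lactate measurement has incremental benefit over conventional maternal vital sign assessment in the diagnosis of sepsis". Section 5.2 fixes the test: "A lactate >2mmol/L will indicate sepsis", and "For tests combining vital signs and lactate, both will need to indicate sepsis to give a positive test result".

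Section 5.4 sets the endpoints: "The primary outcomes are the absolute differences in sensitivity and specificity between pairs of index tests". The first pair is Day 0 vital signs against Day 0 vital signs plus lactate. Section 7.3 handles the comparison in two unlinked models ("we will fit separate generalized estimating equation (GEE) models for women with and without sepsis to estimate absolute differences in sensitivity and specificity"), with delta-method intervals. It also reports PPV and NPV for each test. Secondary analyses (a) to (c) reuse the Day 0 comparison, with differences again in sensitivity and specificity only.

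Section 7.3 writes out no null hypothesis. Section 6.1 applies two-sided tests "with a p-value of ≤ 0.05 considered to be statistically significant", and section 5.5 justifies the sample size by power to test hypotheses. Comparison with zero is therefore the operative test by implication.

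**The concern.** The question is whether lactate adds information to vital signs. Under the both-positive rule, women positive on the combined test are a subset of those positive on vital signs. Adding lactate can only remove positives: some true, which costs sensitivity, and some false, which gains specificity. A zero difference in specificity then means that no vital-sign-positive woman without sepsis has lactate at or below 2 mmol/L. It does not mean that lactate fails to discriminate.

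An uninformative second test would therefore produce a specificity gain and a sensitivity loss, and both could be significant. A reader could take the gain as support for adding lactate to the FAST-M trigger, or the loss as evidence against it, when neither sign could have come out otherwise. Because women with and without sepsis are modelled separately, no planned contrast asks whether false positives are removed at a higher rate than true positives.

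**Working it through.** **Inputs from the SAP.** N = 500, prevalence 40%, vital-sign sensitivity 30–60%, specificity 75% or 90%, a precision calculation on 200 women without sepsis, and up to 346 participants for power (all section 5.5); two-sided 5% level (6.1).

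**Assumed.** q = P(lactate >2 mmol/L), the same with and without sepsis, ranged over 0.2–0.9. The SAP gives no figure for it.

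**The plan's own 346.** For a paired comparison of independent tests, n = (1.96 + 1.282)² × disc / d². The worst case is 40% to 60%: disc = 0.4×0.4 + 0.6×0.6 = 0.52 and d = 0.20, so n = 10.51 × 0.52 / 0.04 ≈ 137 with sepsis, and 137/0.4 ≈ 342. A continuity-corrected unpaired formula gives 140/0.4 = 350. Both lie within 3% of 346. The first lets discordant pairs run in both directions and the second ignores pairing; neither describes nested tests.

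**Expected change when lactate is noise.** Specificity gain = (1 − specificity)(1 − q). Sensitivity loss = sensitivity × (1 − q).

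| | q = 0.2 | 0.5 | 0.8 | 0.9 |
|---|---|---|---|---|
| gain, specificity 75% | 20 points | 12.5 | 5 | 2.5 |
| gain, specificity 90% | 8 points | 5 | 2 | 1 |

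**How often this is significant.** All discordant pairs run one way, so their number b is Binomial(n, P(vital signs positive) × (1 − q)). The Wald statistic is √(b/(1 − b/n)). With n = 300, b = 3 gives 1.74 and b = 4 gives 2.01, so the test rejects at b ≥ 4; the same cut-off holds for n = 200 and n = 138. Exact binomial tails for specificity:

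| women without sepsis | specificity | q = 0.5 | 0.7 | 0.8 | 0.9 |
|---|---|---|---|---|---|
| 300 (N = 500) | 75% | 100% | 100% | 99.98% | 94% |
| 300 (N = 500) | 90% | 99.98% | 98% | 85% | 35% |
| 200 | 75% | 100% | 99.99% | 99.1% | 74% |
| 200 | 90% | 99.1% | 85% | 57% | 14% |

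For q = 0.2 every row is at least 99.9%. For sensitivity at N = 500 (200 with sepsis), rejection is 99.8% or more for q of 0.2–0.8. Simulating the GEE with robust variance agreed (specificity 90%, 200 women: 98.8% at q = 0.5 and 60.8% at q = 0.8). Exact McNemar is lower (same setting: 93.8% and 21.3%).

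**A contrast that does separate the cases.** Let r = P(lactate >2 | vital signs positive, sepsis) / P(lactate >2 | vital signs positive, no sepsis). The odds of sepsis among combined-test positives equal the odds among vital-sign positives times r, so PPV rises only if r > 1.

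Example: sensitivity 60%, specificity 75%, prevalence 40%, q = 0.5.
- Sensitivity falls to 30% and specificity rises to 87.5%.
- PPV is 0.24/(0.24 + 0.15) = 61.5% before and 0.12/(0.12 + 0.075) = 61.5% after.
- NPV falls from 0.45/(0.45 + 0.16) = 73.8% to 0.525/(0.525 + 0.28) = 65.2%. NPV therefore shows the cost of the rule, while PPV carries the information question.

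A score test of r = 1 rejects in 4.7–5.4% of studies under the noise scenario.

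**The case against.** The strongest reply is that section 7.3 promises estimates with intervals and names no rule under which a specificity gain counts as benefit. A reader might infer that the plan will declare benefit from a significant specificity result; the SAP does not say so. Sensitivity is co-primary, so a worthless lactate would show a visible loss beside the gain. PPV and NPV are reported per test, and an unchanged PPV would be visible. All of this stands. It narrows the point to the meaning of a departure from zero and the lack of a contrast joining the two differences.

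A reader might also infer that a noise lactate is significant almost always. That fails at specificity 90% with high q, as the table shows, and q is not in the SAP. The forced sign does not depend on q.

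A third tempting reading is that section 5.4, where one outcome begins "The predictive value of vital signs (Day 0) alone compared to that of vital signs (Day 0) + lactate (Day 0) in those without sepsis at", contradicts section 7.3, which plans no PPV or NPV difference. Predictive value there may simply mean prognostic performance, so this is not a clear contradiction.

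Finally, r > 1 does not establish benefit. With assumed lactate positivity of 30% v 10%, sensitivity 60%, specificity 75% and N = 500, a log-ratio Wald lower limit exceeds 1 in about 92% of studies while sensitivity falls from 60% to 18%. Section 2 wants a sensitive trigger. The ratio also says nothing about vital-sign-negative women.

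**Conclusion.** The concern holds in a limited form. For the Day 0 comparison, section 5.2 determines the sign of both primary differences, so an interval excluding zero cannot tell an informative lactate from an uninformative one. With a noise lactate at N = 500, the specificity gain is significant in about 85–100% of studies for q of 0.2–0.8. It is 35% at specificity 90% with q = 0.9, and with 200 women without sepsis at that specificity it is 57% at q = 0.8 and 14% at q = 0.9. These figures rest on the assumed q and on the sensitivities and specificities in section 5.5.

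It does not follow that the differences or their intervals are invalid: they describe the trade-off correctly. What is missing is a planned contrast that answers the question in section 2.

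A related inconsistency comes first. Section 5.5 powers a 20-point rise in sensitivity over vital signs alone and guards against more false positives. Neither can occur for the Day 0 pair under section 5.2.

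**What to change.** 1. Reconcile section 5.2 with section 5.5 first. The items below apply if the both-positive rule stands.
2. In section 7.3, keep the sensitivity and specificity differences with their intervals. State that, for Day 0 vital signs against Day 0 vital signs plus lactate, departure from zero is not evidence that lactate is informative.
3. Add a paired comparison of PPV (with NPV) between the two tests, or equivalently to the PPV contrast the ratio r with a score-based 95% interval. Do this for the primary analysis and for secondary analyses (a) to (c), each with its own reference standard.
4. State that r above 1 is necessary evidence that lactate discriminates among vital-sign-positive women, is not sufficient for benefit, and is to be read beside the sensitivity loss.

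Cost: SAP wording and one extra contrast per analysis, with no new data or participants. The contrast uses only vital-sign-positive women: at N = 500, 60–120 with sepsis plus 30–75 without, so 90–195. Under an assumed 60% v 30% lactate positivity, score-test power at N = 500 is about 94–99% at specificity 75% and 78–85% at 90%. At N = 346 and specificity 90% it is about 61–70%. A Wald limit on the log ratio would do worse at specificity 90% (69–75% at N = 500, 46–52% at about N = 346), hence the score interval.
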